#### 8.5. The role of the sponsor

## 8.5.1. Analysis of serious adverse events

The sponsor must evaluate:

- the cause of SAEs (all adverse events, for which the investigator or sponsor considers that a causal relationship with the investigational drug(s) can be reasonably envisaged, are considered as suspected serious adverse events. In the event of a different assessment by the sponsor and the investigator, both opinions are mentioned on the report sent to the competent authority if such a report is necessary),
- and whether they are expected or unexpected, with the help of the reference document (investigator's brochure, package insert or SmPC) in force.

## 8.5.2. Transmission of annual safety reports

On the anniversary date of the trial authorization issued by the Health Authorities, the sponsor draws up a safety report that complies with the specifications, including in particular:

- a list of serious adverse events likely to be associated with the investigational drug(s), including unexpected and expected serious adverse events,
- a concise, critical analysis of patient safety for research purposes.

It is sent to the competent authorities (ANSM) and the EC within the regulatory deadlines.

### 8.5.3. Supervisory Board

The mission of the Independent Monitoring Committee is to monitor the clinical and biological safety of the study treatments. It is responsible for providing information to help the sponsor to make decisions whether to amend or discontinue the trial. It is set up at the start of the study and comprises at least 3 members not directly involved in the trial.

The Supervisory Board transmits its recommendations to the sponsor who decides whether or not to stop the study. A decision may be made to stop the study earlier if it appears contrary to the rules to continue (occurrence of serious adverse events, publication of the results of a trial providing the answer to the question asked, etc.).

# 8.5.4. Methods and duration of follow-up of participants following the occurrence of undesirable events

Each adverse event will be monitored until its complete resolution (stabilization at a level deemed acceptable by the investigator, or return to the previous state), even if the patient is withdrawn from the trial.

9.1. Description of planned statistical methods, including schedule of planned interim analyses

The main analysis will be "intention to treat". It will be supplemented by a "per-protocol" analysis. No interim analysis is planned.

# Primary endpoint:

The VAS on activity at 3 months will be compared between groups using a mixed model, taking account of the initial VAS as a fixed effect and the center as a random effect.

# Secondary endpoints:

- Changes in pain at rest and during activity over time will be compared between groups, using random-effects models to account for inter-individual variability modeled via random effects (based on the idea that patients represent a random sample from a larger population), as well as intra-individual variability modeled via measurement error; the group effect (HA + CTC vs. CTC alone), time (M0, M1, M3, M6, M12) and their possible interaction will be estimated and tested.
- Changes in **Cochin scale** parameters, **grip strength** and **opposition strength over** time will be compared between groups using random-effects models. The effect of group (HA + CTC vs. CTC alone), time (M0, M1, M3, M6, M12) and their possible interaction will be estimated and tested.
- The proportion of patients with a change in **ultrasound score** between D0 and M3 will be compared between groups using a Chi2 test.
- The VAS of pain at the time of injection will be compared between the two groups using a Student's t test.
- The number of **new infiltrations** during the follow-up year will be compared between groups using a Student's t test.
- Adverse events will be described for each group in terms of numbers and percentages.
- Changes in **analgesic use** will be compared between groups using random-effects models. The group effect (HA + CTC vs. CTC alone), time (M0, M1, M3, M6, M12) and their possible interaction will be estimated and tested.
- The number of days **off work** during the follow-up year will be compared between groups using a Student's t test.
- The rate of patients undergoing **surgery** will be compared between groups using a Chi2 test.

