#### 2.6. Description of the study population

The target population for this study is patients over 40 years of age who consult the rheumatology departments of the participating centers, and who experience pain that is resistant to standard medical treatment with NSAIDs, ice application or analgesics, and with a VAS greater than or equal to 4 with activity.

Selection procedures are described in Chapter 5.

Patients who participate in the RHIZ'ART study may not simultaneously participate in any other interventional research (except interventional research with minimal risks and constraints) for the duration of their participation in the study (i.e., 12 months).

2.7. References to scientific literature and relevant data for research purposes See Appendix 1

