#### 3.2. Secondary objectives

- Comparison of the changes in pain with activity at M1, M6 and M12 and of the most intense pain.

- Comparison of pain between M0 and M3, by weekly recording of a VAS score.
- Comparison of the changes in pain at rest at M0, M1, M3, M6 and M12 and of the most intense pain.
- Comparison of the changes in function with the Cochin hand scale at M1, M3, M6 and M12.
- Comparison of grip and opposition strength changes at M1, M3, M6 and M12.
- Description of ultrasound changes.
- Comparison of injection pain.
- Comparison of the patient's perception of the changes in pain at 3 months.
- Comparison of new infiltrations.
- Description of adverse effects and events.
- Description of analgesic and NSAID use.
- Comparison of the after-effects of infiltration.

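### The longitudinal secondary models specify only random effects plus measurement error; if that means a random intercept and correlation fades over 12 months, visit contrasts miss the nominal 5%, low at M1 and high at M12

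*Combined protocol and SAP*

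**What the plan says.** Section 9.1, under Secondary endpoints, compares rest and activity pain over time "using random-effects models to account for inter-individual variability modeled via random effects", "as well as intra-individual variability modeled via measurement error". It lists the group effect, "time (M0, M1, M3, M6, M12") "and their possible interaction will be estimated and tested". For the Cochin scale, grip strength, opposition strength and analgesic use it names random-effects models with the same three effects and does not describe the residual part.

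The section does not say whether the random effects are an intercept alone or an intercept and slope. It names no serial correlation, no variance that differs by visit, no unstructured covariance and no robust standard error. It writes no contrast at a given visit. Section 3.2, however, sets visit-specific objectives, such as "Comparison of the changes in pain with activity at M1, M6 and M12", and lists function and strength at M1, M3, M6 and M12.

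Section 9.3 sets significance at 5%. Section 2.6 describes patients "with a VAS greater than or equal to 4 with activity", so activity pain has an entry floor at M0 that later visits lack.

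**The concern.** Random effects plus measurement error is the usual description of a model whose residuals are independent with one common variance. With a patient intercept alone, that model forces the same variance at every visit and the same correlation between M0 and M1 as between M0 and M12. This trial gives reasons to doubt both. The visits are unequally spaced over a year, section 2.2 calls the course of the pain fluctuating, further corticosteroid infiltrations are allowed (section 4.2.2.3), and M0 activity pain is truncated from below.

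If correlation fades with time, one pooled residual variance is too large for a change over one month and too small for a change over twelve. Section 2.2 expects a rapid corticosteroid effect and a slower, more lasting hyaluronic acid effect. M1 and M12 are therefore the informative secondary visits, and they are the two that such a model would distort most, with lost power at M1 and false positives at M12. Moving M0 from outcome to covariate does not cure this: in the settings below the random-intercept sizes are then 1.6-2.4% at M1 and 8.3-8.9% at M12.

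**Working it through.** **The plan's own figures.** Section 9.2 gives a baseline of 6.4 (SD 1.3) and reductions of 25% and 35%, a difference of 0.10 × 6.4 = 0.64. The normal formula gives 2 × (1.960 + 0.842)² × 1.3² / 0.64² = 64.8, so 65 per arm or 130. The t version gives 66 per arm, which is the stated 132; adding 18 gives 150. For the longitudinal models the only stated figure is the 5% level, taken here as two-sided.

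**Inputs.** From the documents: visits at 0, 1, 3, 6 and 12 months, 1:1 allocation, 150 patients, M0 SD 1.3. Assumed: visit as a category, complete data, and correlation between two visits of b × φ^(months apart), with (b, φ) = (0.75, 0.95), (0.80, 0.92) and (0.80, 0.88). These give 0.70-0.74 at one month and 0.41, 0.29 and 0.17 at twelve. SDs are either equal at all visits or 1.3 at M0 and 2.2 afterwards; the 2.2 is assumed.

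**Formulas.** Let S be the true 5 × 5 covariance of a patient's scores. A random-intercept fit estimates the residual variance as s² = (trace S − sum of all elements of S / 5) / 4 and gives every change from M0 the variance 2s². With r = true variance of the change / 2s², the true size is 2 × (1 − Φ(1.96/√r)). The number per arm cancels from r, so a larger trial does not help.

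**One setting in full: (0.80, 0.92), equal SDs of 1.**
- Correlation with M0: 0.80 × 0.92 = 0.736 at M1; 0.80 × 0.92¹² = 0.294 at M12.
- The elements of S sum to 15.296, so s² = (5 − 15.296/5)/4 = 0.485 and 2s² = 0.970.
- M1: true variance 2 × (1 − 0.736) = 0.528, r = 0.544, 1.96/√0.544 = 2.657, size 0.8%.
- M12: true variance 2 × (1 − 0.294) = 1.412, r = 1.455, 1.96/√1.455 = 1.625, size 10.4%.
- Power at M1: an effect with true 80% power (1.960 + 0.842 = 2.802 standard errors) must clear 2.657, so power is Φ(2.802 − 2.657) = Φ(0.145), about 56%. Over the three equal-SD settings it is 52-65%.

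**Size (%) at nominal 5%, range over the three settings.** The random-slope rows use the best-fitting intercept-and-slope covariance in place of the intercept-only one. The last column is the joint 4-df interaction test.

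| Fitted model; true SDs | M1 | M3 | M6 | M12 | Joint |
|---|---|---|---|---|---|
| Intercept; equal | 0.6-1.6 | 2.6-3.1 | 5.4-6.0 | 9.4-10.4 | 5.7-6.2 |
| Intercept; 1.3 then 2.2 | 0.5-1.4 | 1.7-2.3 | 3.6 | 6.1-6.5 | 5.7-6.2 |
| Intercept + slope; equal | 1.8-3.2 | 4.9 | 6.0-6.8 | 4.1-4.4 | 5.1-5.4 |
| Intercept + slope; 1.3 then 2.2 | 1.3-2.5 | 3.0-3.4 | 4.0-4.1 | 2.5-2.9 | 5.3-5.7 |

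**Other true covariances, random-intercept fit.**
- Compound symmetry: 5.0% at every visit.
- Constant correlation 0.5, SD 1.3 at M0 and 2.3 later: 3.2% at every visit.
- Pure decay of 0.9 per month, equal SDs: M1 0.01%, M12 13.4%, joint 7.7%. At 0.95 per month the joint test reaches 8.2%.

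**The case against.** A reader might infer that the plan tests late contrasts above 5% as a matter of fact. The documents do not support that, for five reasons.

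1. The words constant and independent are not in section 9.1; they are the usual reading of its wording. The measurement-error clause belongs to the pain models alone, so extending it to Cochin, strength and analgesic use is a further inference.
2. Random effects is plural and a slope is not excluded. With one, M12 is no longer above 5% in any of the settings above.
3. No between-visit correlation and no follow-up SD is given. Compound symmetry gives exactly 5%.
4. The entry floor does not support late inflation. A smaller M0 SD lowers the M12 size from about 10% to 6.1-6.5%, and with constant correlation 0.5 it gives 3.2% throughout.
5. The tests that section 9.1 names are group, time and interaction. The joint interaction test moves little, and no rule makes an M12 contrast the basis for a claim.

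All five stand, and they limit the claim to a conditional one. They do not show that the text is adequate. Section 3.2 asks for comparisons by visit, and these models are the only planned route to most of them. Of the two natural readings, neither gives even error rates when correlation fades: with a slope, M1 stays at about 1-3% and M6 ranges from about 4% to 7%.

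**Conclusion.** The point holds in conditional form. Section 9.1 gives the pain models a structure that, on its ordinary reading, makes no allowance for fading correlation or unequal variance, and it gives the other longitudinal outcomes no residual structure at all. If the model is a random intercept and correlation falls from about 0.7 at one month to 0.2-0.4 at twelve, change-from-M0 contrasts have a size of about 0.5-1.6% at M1 and 6-10% at M12. With a random slope the M12 excess disappears (about 2.5-4.4%) but sizes stay uneven. The joint interaction test is at about 5-6% in these settings and up to about 8% under stronger decay.

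These figures rest on assumed correlations and follow-up SDs, and on complete data. They do not establish that any late contrast in this trial will be inflated. The M3 primary analysis in section 9.1 is a single-time-point model and is unaffected, as are the 132 and 150 patients.

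**What to change.** In section 9.1, replace the description of the longitudinal models by a repeated-measures model for the continuous longitudinal secondary endpoints, with:
- visit as a category and group-by-visit terms;
- an unstructured within-patient covariance and Kenward-Roger degrees of freedom;
- a fallback stated in advance if the model does not converge: heterogeneous Toeplitz with robust standard errors, naming the degrees-of-freedom rule that goes with them;
- a statement that the visit comparisons in section 3.2 are taken from this model.

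Each contrast then uses its own variance. With complete data the test of a change from M0 amounts to comparing the two groups' change scores, so its size is about 5% whatever the true covariance.

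The cost is a few lines of text and a small change of code. Five visits need 5 × 6 / 2 = 15 covariance parameters, or 4 × 5 / 2 = 10 if M0 is a covariate, which 150 patients can support, with slightly fewer degrees of freedom. Making the change before unblinding also removes a choice that would otherwise be made with the data in view.

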In 2006, Fuchs reported similar results, with improvement in pain and function for both types of infiltration in a randomized study of 56 patients. Pain improvement was faster with corticosteroids (significant at 2 weeks) but slightly better with HA at 26 weeks, with a clearer functional gain for HA mainly at 6 months.

In 2008, in a 3-arm study, one of which was placebo, Heyworth made the same findings but with no significant difference with placebo. He noted an improvement in pain and function in

all 3 groups (18 to 22 patients in each), with a clearer improvement in pain for the HA group at 6 months and in function at 3 and 6 months.

Moreover, the latest study in 2015 by Montfort, concludes that "HA was more effective over time and improved functional status more markedly in patients with severe symptoms".

Concerning the number of HA infiltrations to be administered in rhizarthrosis, a French team led by Roux C showed that there was no difference between groups receiving one, two or three infiltrations at one-week intervals, in terms of neither pain nor function.

Therefore, the 2 types of infiltration appear to be effective, but with different response profiles: corticoids have a rapid analgesic and anti-inflammatory action, whereas HA has a more delayed and sustained action over time. Consequently, it seems appealing to combine these 2 treatments to obtain a synergistic effect. One study demonstrated the benefits of this combination in gonarthrosis, which was more effective on pain than hyaluronic acid alone and there was no difference in functional improvement between the two groups.

Some authors have questioned the potential clinical or histological risks of combining these two drugs, given the risk of reduced chondrocyte proliferation and increased apoptosis which could lead to chondral degradation. However, no increased risks have been reported with this combination, neither clinically nor histologically.

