## 4.1.2. Secondary endpoints

- VAS recorded at inclusion, M1, M6 and M12 post-infiltration.
- Recording of VAS between 0 and 3 months.
- This will be done by means of weekly VAS measurements taken by the patient himself/herself, recorded in a notebook given to the patient.
- A VAS of perceived pain at the base of the thumb will be recorded at rest at inclusion, and at 1, 3, 6 and 12 months.
- The worst Pain Score at M0, M1, M3, M6 and M12.
- Cochin score at inclusion, M1, M3, M6 and M12.

This score incorporates the inability to cook, get dressed, wash, work and perform other activities reported by the patient. It ranges from 0 to 90: the higher the score, the greater the impact of the rheumatological pathology on hand function. This index has been validated for its reliability, validity, and sensitivity to change in the arthritic hand.  The questionnaire takes an average of 3 minutes to complete, has an inter-observer correlation of 0.96 and good construct validity. Another advantage of this scale is the capacity to discriminate between improving and deteriorating patients.

- Grip and opposition strength.

Measurements will be carried out using two different JAMAR dynamometers according to a standardized methodology;

The first allows measurement of opposition strength, expressed in kilograms. The thumb-index grip of the dominant and non-dominant hands is measured 3 times. A one-minute rest period is observed between each test. The highest values will be used.

The second measures grip strength in kilograms.

These two strengths will be assessed at inclusion, and at 1, 3, 6 and 12 months.

- Ultrasound evaluation at inclusion and M3.

Initial ultrasound data will be collected at M0 in B and Doppler modes, and at 3 months. The appearance of lesions on ultrasound will be graded as stage I, II or III according to the OMERACT grading principle (Cf appendix 4).

- A VAS recorded during infiltration.
- Verbal score for overall change at 3 months.

The verbal progression scale is a dynamic criterion for assessing disease progression in relation to a given reference. The use of this type of scale is suggested by treatises on the measures to be used in research projects in osteoarthritis, and the scale has proved its effectiveness in a large number of trials. 

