At the 3-month follow-up visit, the patient will be asked to answer the following question: "Today, compared to the start of treatment (M0), I consider that my thumb:"

- o has worsened
- o has stabilized or had zero improvement
- has improved slightly
- has improved moderately
- has improved significantly
- is healing
- The number of corticosteroid infiltrations over the 12 months of follow-up.

- Recording of adverse effects and events over the 12 months of follow-up.
- Recording of analgesic and NSAID use (number of days taken and cumulative dosage over the week preceding each follow-up visit).
- The number of days off work from the start of orthosis use over the 12 months of follow-up.
- Possible progression to a surgical procedure over the 12 months of follow-up.

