### Study schedule:

Actions	M-1 (Pre-inclusion visit)	M0 (Inclusion visit)	M1	М3	M6	M12
Checking inclusion/non-inclusion criteria	X					
Signing the informed consent		X				
History	X					
Clinical examination		X	X	X	X	X
Randomization		X				
VAS at rest		X	X	X	X	X
VAS for thumb-index grip (during activity)		X	X	X	X	X
VAS for infiltration		X				
Worst Pain Score		X	X	X	X	X
Cochin scale		X	X	X	X	X
Verbal score for overall change			X	X	X	X
Dynamometer (2x3 measurements)		X	X	X	X	X
B-mode and Doppler ultrasound		X		X		
Concomitant treatments (analgesics, NSAIDs)		X	X	X	X	X
Adverse events		X	X	X	X	X

\* Weekly VAS for the first 3 months will be recorded in the patient's diary. The use of new infiltrations, the number of days off work and any progression to a surgical procedure will be recorded during the 12 months of follow-up.

The time allowed for visits at M1 and M3 (primary endpoint) is  $\pm$ 4 days. The time allowed for the other follow-up visits (M6 and M12) is  $\pm$ 4 week.

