### 4.3. Description of measures taken to reduce and avoid bias

## 4.3.1. Drawing of lots

Randomization will be blinded to patient and evaluator, with 2 groups of patients: one group receiving an injection of hyaluronic acid combined with corticosteroids, and the other receiving an injection of corticosteroids and 0.9% NaCl. Randomization will be stratified by center. It will be carried out in a 1:1 ratio and in blocks.

Capture System software will be used for randomization by connecting to the website: https://www.dirc-hugo-online.org/csonline/. A login, password and study number will be issued by a data manager in the Research Promotion Department of La Roche sur Yon Hospital. The following information must be provided:

- First initial of the last name,
- First initial of the first name,
- Month and year of birth,
- Compliance with inclusion and non-inclusion criteria (yes/no),
- Signing of the informed consent (yes/no).

Randomization will be carried out by the investigator once the possibility of inclusion in the study has been confirmed and the patient's informed consent has been signed.

The inclusion number will be assigned automatically during randomization. A confirmation e-mail will be sent to the person who carried out the randomization, as well as to all those concerned.

The randomization list will be drawn up by a statistician from the Research Promotion Department of La Roche sur Yon Hospital. An explanatory guide to randomization will be available online in Capture System.

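### The secondary repeated-measures models treat M0 as an ordinary outcome time, so their change-from-M0 contrasts can be less precise than the baseline adjustment used for the primary endpoint

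*Combined protocol and SAP*

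**What the plan says.** Section 9.1 (Secondary endpoints) compares rest and activity pain over time with random-effects models in which "the group effect (HA + CTC vs. CTC alone), time (M0, M1, M3, M6, M12) and their possible interaction will be estimated and tested". The item on Cochin score, grip strength and opposition strength repeats these terms. M0 is thus one of five levels of the outcome's time factor. The section states no baseline covariate and no constraint that the arms share an M0 mean.

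Section 9.1 (Primary endpoint) treats the same pain scale differently. Activity VAS at 3 months is compared "taking account of the initial VAS as a fixed effect and the center as a random effect".

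The objectives are visit-specific. Section 3.2 asks for "Comparison of the changes in pain with activity at M1, M6 and M12", for rest pain at M0, M1, M3, M6 and M12, and for function and strength at M1, M3, M6 and M12. Section 9.1 does not say which model term answers each of these.

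**The concern.** M0 is the inclusion measurement; section 9.1 calls it the initial VAS and section 9.2 the baseline. Taken as pre-injection, it has the same expected value in both randomised arms. An unconstrained model still estimates a separate M0 mean in each arm, and the group-by-time contrast subtracts the chance difference between those means in full. Baseline adjustment subtracts only the part that the M0-to-visit correlation supports.

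What is at stake is precision on secondary endpoints. Section 2.2 describes corticosteroids as fast-acting, "whereas HA has a more delayed and sustained action over time". Differences at M6 and M12 are therefore of real interest, and for these scales only the secondary models estimate them. The M0 values needed for a sharper estimate are already collected.

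**Working it through.** **Inputs from the documents.** Baseline mean 6.4 and SD s0 = 1.3; reductions at 3 months of 25% and 35%; 132 patients required and 150 planned (section 9.2). Allocation is 1:1 (section 4.3.1), so n = 75 per arm.

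**Assumed, because the documents do not give them.** Correlation r between M0 and a follow-up visit: 0.3, 0.5, 0.7. Follow-up SD s1: 1.3, 1.6, 2.0. A value above 1.3 is plausible because the entry criterion of VAS ≥ 4 narrows the spread at M0 but not later. Complete data are assumed.

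**1. The plan's own figure.** 0.35 × 6.4 − 0.25 × 6.4 = 2.24 − 1.60 = 0.64. With SD 1.3, two-sided 5% and 80% power, the normal approximation gives 65 per arm (130), and the t-test calculation gives 66 per arm, which is 132. The stated figure reproduces. It concerns the primary endpoint; no sample size or power is stated for the secondary models.

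**2. What the planned contrast estimates.** With complete data, the group-by-time term at a visit is the difference between arms in mean change from M0. In 150 simulated trials fitted with a random-intercept model, the M3 term and the raw difference in change agreed to about 1e-13.

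**3. Residual variances per visit.**

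- Change from M0: v_c = s0² + s1² − 2·r·s0·s1
- Baseline-adjusted: v_a = s1²·(1 − r²)
- Excess: v_c − v_a = (s0 − r·s1)², never negative and zero only when r·s1 = s0

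Example with s1 = 1.3 and r = 0.3: v_c = 1.69 + 1.69 − 1.014 = 2.366; v_a = 1.69 × 0.91 = 1.538; ratio 0.650.

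**4. Relative efficiency v_a / v_c, activity VAS.**

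| Follow-up SD | r = 0.3 | r = 0.5 | r = 0.7 |
|---|---|---|---|
| 1.3 | 0.650 | 0.750 | 0.850 |
| 1.6 | 0.776 | 0.885 | 0.976 |
| 2.0 | 0.881 | 0.971 | 0.995 |

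In the lowest cell, 75 × 0.65 = 48.75: the change contrast with 75 per arm is worth about 49 per arm with baseline adjustment.

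**5. 95% CI half-widths**, 1.96·√(2v/75), at r = 0.5, change versus adjusted:

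- s1 = 1.3: 0.416 v 0.360
- s1 = 1.6: 0.471 v 0.443
- s1 = 2.0: 0.563 v 0.554

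These need no assumed treatment effect.

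**6. Checks on the remedy.** With equal SDs of 1.3, exact generalised least squares gives SEs for the unconstrained contrast of 0.251, 0.212 and 0.164 at r = 0.3, 0.5 and 0.7. A common M0 mean gives 0.203, 0.184 and 0.152, the same as baseline adjustment. A simulation of 10,000 trials per setting (r = 0.5, three centres, assumed centre SD 0.5) gave change-contrast SEs of 0.215, 0.238 and 0.290 for s1 = 1.3, 1.6 and 2.0, identical with and without a centre term. Baseline adjustment with centre gave 0.186, 0.224 and 0.286.

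**The case against.** The strongest defence is that nothing here is wrong. A repeated-measures model with M0 as an outcome is a valid analysis of change, its contrasts are unbiased, and adjusting one primary endpoint does not oblige every secondary model to follow. The size of the loss also rests on two quantities the documents do not give, and the entry criterion points away from the least favourable row of the table. All of that stands, and it limits this point to efficiency. It does not make the choice neutral: the excess variance cannot be negative, and the data that remove it are already collected.

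Two cost objections carry less weight. Visit-by-visit reporting adds no comparisons beyond those section 3.2 already plans. Losing patients who lack an M0 value is avoided by the common-mean version.

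Several stronger readings are tempting but unsupported:

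- **That no treatment comparison is specified.** Section 9.1 names the arms and section 3.2 the visits; only the link to a model term is missing.
- **That the interaction may be dropped**, leaving one five-time group effect that shrinks a sustained difference to four fifths. Section 9.1 says the interaction will be estimated and tested, and no rule for removing it appears.
- **That a stated amount of power is lost at M1, M6 or M12.** The 25% and 35% reductions are for 3 months; no effect is given for other visits.
- **That the missing centre term causes the loss.** Randomisation is stratified by centre and the primary model includes it, so the omission is inconsistent, but the change-contrast SE was the same either way.

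**Conclusion.** The point holds as a free improvement to secondary analyses. As written, the models for rest and activity pain, Cochin score, grip strength and opposition strength yield change-from-M0 contrasts that are unbiased but, in large samples, never more precise than baseline adjustment. For activity VAS the relative efficiency runs from 65% to over 99% across the assumed correlations and follow-up SDs. At the upper end the two methods are practically the same; at the lower end the difference is substantial. The range rests on the baseline SD of 1.3, complete data, M0 being measured before injection, and the assumed r and s1. The documents give no SD for rest pain, Cochin score or strength, so no size can be stated for them. The primary analysis and the 132/150 sample size are unaffected.

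**What to change.** In section 9.1, for each of these continuous repeated endpoints:

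- Model M1, M3, M6 and M12 with the M0 value as a covariate, its slope allowed to differ by visit. Alternatively, keep M0 as an outcome with a common mean in both arms and let variances and correlations differ by visit; this retains patients without an M0 value.
- Include visit, group and group-by-visit.
- Report the HA + CTC minus CTC + saline difference with 95% CI at the post-injection visits named in section 3.2, labelled as secondary.
- State that the existing primary model remains the only primary analysis of activity VAS at M3.

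Two optional clarifications can go into the same edit. A centre term would match section 4.3.1 ("Randomization will be stratified by center") and the primary model. For analgesic use, section 4.1.2 defines the measure as "number of days taken and cumulative dosage over the week preceding each follow-up visit", while section 9.1 lists M0 as a time level. The study schedule ticks these treatments at M0 without showing that the same quantity is recorded, so the plan should say what the M0 value is, or that M0 is not a time level for this outcome.

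The cost is a change of wording before the data are analysed, with no new data or visits. Because the methods sit in the protocol, the sponsor must decide whether the edit is a substantial modification under section 12.2.
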